3. DESCRIPTION OF DESIGN AND STUDY POPULATION

3.1 OVERALL TRIAL DESIGN AND PLAN

This is a phase I/II prospective multicenter trial to investigate the efficacy and safety of the combination of cetuximab and nivolumab. The cetuximab 500 mg/m² every 2 week dosing schedule in patients with recurrent and/or metastatic HNSCC has been evaluated by a multicenter randomized prospective phase II study and has been shown to have efficacy and toxicity similar to a conventional dosing schedule of 500 mg/m² loading dose followed by 250 mg/m² every week. 9,52

In the phase I portion of the study, patients with recurrent and/or metastatic HNSCC will be treated at:

 Dose level 1: Lead-in cetuximab 500 mg/m² alone (Day -14 of Cycle 1 only) followed by nivolumab 240 mg IV + cetuximab 500 mg/m² every 2 weeks for 24 cycles or discontinuation per section 3.3.4. Dose level -1: Lead-in cetuximab 500 mg/m² alone (Day -14 of Cycle 1 only) followed by nivolumab 240 mg IV + cetuximab 250 mg/m² every 2 weeks for 24 cycles or discontinuation per section 3.3.4.

Each cycle is 4 weeks. Cetuximab is given alone in lead-in period at Day -14 of Cycle 1 only. In all subsequent doses starting on Cycle 1 Day 1, nivolumab and cetuximab will be given concurrently. Dose-limiting toxicities (DLT) will be assessed with the initiation of combination therapy (Cycle 1 Day 1) and will continue for the duration of Cycle 1 (4 weeks).

Pre-medication with steroids before cetuximab and/or nivolumab is not permitted in this trial.

Non-steroidal pre-medications are permitted, including:

Study Number: MCC 19178 IND#: Exempt

- Diphenhydramine 50 mg PO or IV (or equivalent dose of antihistamine such as cetirizine).
- Acetaminophen 500-1000 mg PO (or equivalent dose of antipyretic such as paracetamol).

Dose level 1 has been confirmed as the recommended phase 2 dose, therefore the phase II dosing is dose level 1 at the start of treatment, as discussed below in section 3.2.2.

3.2. DISCUSSION OF STUDY DESIGN

3.2.1. Phase I

This is designed to determine the safety of the cetuximab and nivolumab administration. The purpose of having a lead-in period with cetuximab monotherapy (Day -14 before Cycle 1 only) is to exclude patients with cetuximab-related hypersensitivity reaction before assessing the DLT of the combination regimen.

Eligible patients will begin with a 14-day period with cetuximab alone (Day -14 before Cycle 1 only). This will be followed by subsequent doses of cetuximab and nivolumab starting on Cycle 1 Day 1 IV every 2 weeks in 28-day cycle for 24 cycles or discontinuation per section 3.3.4.

An MRI or CT of neck will be performed approximately every 6 weeks during Cycle 1-3, every 8 weeks during Cycle 5-6 and then every 12 weeks during Cycle 7-24.

3.2.2. Phase II

On April 04, 2018, an analysis of 3 evaluable patients treated at Dose Level 1 was submitted to Moffitt's Protocol Monitoring Committee, documenting that all 3 patients had completed the DLT evaluation period without experiencing any DLT's. As such, Dose Level 1 was declared the maximum tolerated dose (MTD) or the recommended phase II dose of cetuximab and accrual to the phase II portion began under Dose Level 1.

3.2.3. Number of Centers

Three sites are involved.

3.2.4. Number of Participants

Phase I: 3-12 patients

Phase II: Cohort A - 45* patients (42 + 3 or 39 + 6)**

* 45 evaluable patients will be treated at the MTD. In order to be considered evaluable, patients must complete the lead-in period and receive the C1D1 doses of cetuximab and nivolumab. Non-evaluable subjects will be replaced.

IND#: Exempt

** Patients treated at the MTD in the phase I portion of the study will be counted as a part of the phase II patient population.

Phase II: Cohort B - 43 patients

* 43 evaluable patients will be treated in Cohort B. In order to be considered evaluable, patients must complete the lead-in period and receive the C1D1 doses of cetuximab and nivolumab. Non-evaluable subjects will be replaced.

3.3. SELECTION OF STUDY POPULATION

3.3.1. Main Diagnosis for Study Entry

All patients included in this trial must have recurrent and/or metastatic HNSCC.

3.3.2. Inclusion Criteria

Study Number: MCC 19178

Patients must have histologically or cytologically confirmed squamous cell carcinoma
of oral cavity, oropharynx, paranasal sinuses, nasal cavity, hypopharynx, or larynx.
Squamous cell carcinoma of unknown primary in cervical lymph node can be included
only if p16 status is positive.

Cohort A:

- Patients must have recurrent or metastatic HNSCC that is not amenable to local therapy with curative intent (surgery or radiation therapy with or without chemotherapy).
- Patients with persistent disease following radiation therapy administered with a chemotherapy sensitizer may also be included.
- Patients must have progressed on at least one prior line of chemotherapy, targeted therapy, palliative radiation and/or biological therapy regimen for their recurrent and/or metastatic HNSCC. However, if patients are likely to be intolerant to standard first-line systemic chemotherapy, the patients are eligible to enroll to this study as the first-line therapy. Additionally, patients with persistent disease or platinum-refractory recurrent disease (recurs within 6 months of last dose of chemotherapy given as a sensitizer to definitive radiation) may enroll in this study as a first-line therapy.
- Prior treatment with a combination of cetuximab and a PD-1/PD-L1 inhibitor is excluded. Prior treatment with cetuximab or a PD-1/PD-L1 inhibitor is allowed as long as not previously given in combination.

Cohort B:

- Patients must have recurrent or metastatic HNSCC that is not amenable to local therapy with curative intent (surgery or radiation therapy with or without chemotherapy).
- Patients with persistent disease following radiation therapy administered with a chemotherapy sensitizer may also be included.
- Patient must NOT have any systemic therapy for recurrent and/or metastatic disease except if given as a part of a multimodality treatment (i.e. re-irradiation and systemic therapy for curable intent of locally recurrent disease).
- Patients that refuse potentially curative salvage surgery for recurrent disease are ineligible.

- Prior treatment with a combination of cetuximab and a PD-1/PD-L1 inhibitor is NOT included.
- Prior treatment with a PD-1/PD-L1 inhibitor is NOT included.

IND#: Exempt

- Prior treatment with cetuximab or EGFR inhibitors given concurrently with radiation as a radiation sensitizer is included. However, cetuximab or EGFR inhibitors given in the recurrent and/or metastatic setting is NOT included.
- Patients must have measurable disease, defined as at least one lesion that can be accurately measured in at least one dimension (longest diameter to be recorded) as outlined in RECIST version 1.1.
- Patients must be ≥ 18 years of age.
- Life expectancy of greater than 3 months.
- ECOG performance status ≤ 2

Study Number: MCC 19178

- Patients must have normal organ function as defined below:
 - Absolute neutrophil count > 1,500/µL
 - Hemoglobin > 9 g/dL
 - Platelets > 100,000/µL
 - Total bilirubin ≤ 1.5 mg/dL X institutional upper limits of normal (ULN)
 - AST (SGOT)/ALT (SGPT) ≤ 3 X institutional ULN (or 5.0 X the ULN in the setting of liver metastasis)
 - Serum creatinine of ≤ 1.5 X ULN or creatinine clearance > 40 mL/minute (using Cockcroft/Gault formula): Female creatinine clearance = (140 age in years) x weight in kg x 0.8572 x serum creatinine in mg/ dL; Male creatinine clearance = (140 age in years) x weight in kg x 1.0072 x serum creatinine in mg/dL.
- Because the teratogenicity of cetuximab is not known, the patient, if sexually active, must be postmenopausal, surgically sterile, or using effective contraception (hormonal or barrier methods).
- Female patients of childbearing potential must have a negative serum pregnancy test within 7 days prior to enrollment.
- Ability to understand and the willingness to sign a written informed consent document.

3.3.3. Exclusion Criteria

- Patients who experienced grade 3 or above skin toxicity from prior EGFR inhibiting therapy.
- Patients who have experienced grade 3 or above toxicity from prior anti-PD1 therapy.
- Patients who have p16 negative squamous cell carcinoma of unknown primary in cervical lymph node.
- Patients with primary nasopharynx or salivary gland cancers are excluded.
- Patients who have had chemotherapy, biological therapy or definitive radiation within 4 weeks of the study enrollment or those who have not recovered from adverse events to ≤ Grade 1 due to agents administered more than 4 weeks earlier.
- Patients who had undergone any major surgery within 4 weeks of study enrollment.
- Patients who had undergone any palliative radiation within 2 weeks of study enrollment.
- Patients who have had other investigational agents within 4 weeks or 5 half-lives, whichever is shorter, of the study enrollment.
- Patients who have known leptomeningeal metastases or untreated or symptomatic brain metastases. Treated, asymptomatic brain metastasis can be included.
- Uncontrolled intercurrent illness including, but not limited to, ongoing or active infection, autoimmune disease requiring systemic steroids, symptomatic congestive heart failure, unstable angina pectoris, cardiac arrhythmia, or psychiatric illness/social situations that would limit compliance with study requirements.

Subjects with a condition requiring systemic treatment with either corticosteroids (> 10 mg daily prednisone equivalents) or other immunosuppressive medications within 14 days of study drug administration. Inhaled or topical steroids and adrenal replacement doses > 10 mg daily prednisone equivalents are permitted in the absence of active autoimmune disease.

IND#: Exempt

- The patient has clinically relevant coronary artery disease or history of myocardial infarction in the last 12 months or high risk of uncontrolled arrhythmia or uncontrolled cardiac insufficiency.
- The patient has uncontrolled or poorly controlled hypertension (>180 mmHg systolic or > 130 mmHg diastolic) at the time of enrollment.
- The patient has a history of allergic reactions attributed to compounds of chemical or biologic composition similar to those of cetuximab and/or nivolumab.
- The patient is pregnant or breast-feeding.
- Patients with known active HIV, Hep B, or Hep C infection will be excluded. If not clinically indicated, the patients do not need to be tested.

3.3.4. Discontinuation Criteria

Study Number: MCC 19178

Patients will be removed from study when any of the following criteria applies:

- Patients with grade 3 or 4 infusion reaction must not receive further treatment with cetuximab.
- Patients with grade 3 or 4 infusion reaction must not receive further treatment with nivolumab.
- Patients with grade 4 hypertension must not receive further treatment with cetuximab.
- If treatment is interrupted for more than 12 consecutive weeks, patient's protocol treatment will be discontinued.
- Extraordinary Medical Circumstances: If at any time the constraints of this protocol
 are detrimental to the patient's health, the protocol treatment should be discontinued.
- If patient develops progressive disease, then the patient will discontinue the protocol therapy.
- If patient develops unacceptable toxicity, then the patient will discontinue the protocol therapy.
- Patients may withdraw consent and withdraw from the study at any time for any reason
- The reason and date for patient removal from the study must be documented in the Case Report Form (CRF).

3.3.5. Premature Discontinuation of the Study as a Whole

Those who discontinue protocol therapy early will be followed for response until progression and for survival for 2 years from the End of Treatment. Patients removed from study for unacceptable adverse events will be followed until resolution or stabilization of the adverse event.

4. TREATMENTS

4.1. CETUXIMAB LEAD-IN PERIOD

Cetuximab will be administered intravenously starting on Day -14 before Cycle 1 only as lead-in period. Starting dose is 500 mg/m² administered with acetaminophen and a histamine H1-receptor antagonist such as cetirizine. Premedication with steroid will not be allowed.

4.1.1. Definition of Cetuximab Lead-In Toxicity

Study Number: MCC 19178

Patients with grade 3 or 4 infusion reaction must not receive further treatment with cetuximab.

IND#: Exempt

4.2 COMBINATION OF CETUXIMAB AND NIVOLUMAB

4.2.1. Phase I

During phase I, patients will be enrolled sequentially and treated at one of the dose levels identified below.

- Dose Level 1: Lead-in cetuximab 500 mg/m² alone (Day -14 before Cycle 1 only) followed by nivolumab 240 mg IV + cetuximab 500 mg/m² every 2 weeks for 24 cycles or discontinuation per section 3.3.4.
- Dose Level -1: Lead-in cetuximab 500 mg/m² alone (Day -14 before Cycle 1 only) followed by nivolumab 240 mg IV + cetuximab 250 mg/m² every 2 weeks for 24 cycles or discontinuation per section 3.3.4.

Each cycle is 4 weeks. Cetuximab is given alone in lead-in period at Day -14 before Cycle 1 only. In all subsequent doses starting Cycle 1 Day 1, nivolumab and cetuximab will be given concurrently. DLT assessment will be performed during Cycle 1 and will start with the initiation of the combination of cetuximab and nivolumab (4 weeks).

4.2.2. Phase II

On April 04, 2018, an analysis of 3 evaluable patients treated at Dose Level 1 was submitted to Moffitt's Protocol Monitoring Committee, documenting that all 3 patients had completed the DLT evaluation period without experiencing any DLT's. As such, Dose Level 1 was declared the maximum tolerated dose (MTD) or the recommended phase II dose of cetuximab and accrual to the phase II portion began under Dose Level 1.

4.2.3. Definition of Dose-Limiting Toxicity of Cetuximab and Nivolumab

The phase I of the study will enroll 3 to 6 patients per dose level using a standard 3+3 design. The DLT period will start on Cycle 1 Day 1 of cetuximab and nivolumab and end on Cycle 1 Day 28. The toxicity after the lead-in cetuximab (Day -14 before Cycle 1 only) prior to the dosing of cetuximab and nivolumab will not be included to the assessment of DLT (Day -14 to Day -1).

The MTD will be determined using the following de-escalation rules:

- A cohort of three patients will be entered at Dose Level 1.
- If none of these patients experiences a DLT (see below for the criteria) during Cycle 1 (4 weeks), Dose Level 1 will be the recommended dose for Phase II.
- If 1 of these 3 patients experiences a DLT, 3 more patients will be enrolled at Dose Level 1. If 1 of 6 patients at this dose level experiences a DLT, the phase II dose will be Dose Level 1. If 2 or more DLTs occur within Dose Level 1, then the MTD will have been exceeded, and 6 new patients will be enrolled at Dose Level -1.
- If ≤1 of 6 patients at Dose Level -1 experiences a DLT, the phase II dose will be Dose Level -1. If 2 or more DLTs occur within Dose Level -1, then the MTD will have been exceeded. This combination is determined to be unsafe to conduct the phase II portion of the trial and the trial will be discontinued.

The target DLT rate is <25%. The MTD will be defined as the dose of cetuximab and nivolumab in which <1 of 3 patients experience a DLT or <2 of 6 patients experience a DLT with the next higher dose having at least 2 patients experiencing a DLT. The MTD is the highest dose at which at most 1 of 6 patients has a DLT.

IND#: Exempt

No dose escalations or de-escalations are permitted within each patient's treatment, although dose delays will be permitted. A patient who is withdrawn from the study before the completion of Cycle 1 for a reason other than a DLT will be replaced.

This study will utilize the Cancer Therapy Evaluation Program Common Terminology Criteria for Adverse Events (CTCAE) version 4.1 for toxicity and event reporting. DLTs will be observed until patients have completed Cycle 1 (4 weeks).

A DLT will be defined as any of the following events:

- Grade 3 or 4 immune-related toxicities, including dermatitis, hepatitis, thyroiditis, colitis, and pneumonitis.
- Grade 4 cetuximab-related rash.

Study Number: MCC 19178

- 3. Grade 3 or 4 neutropenia (i.e., absolute neutrophil count < 1000 cells/mm³) that is associated with a fever ≥ 38.5°C or lasting longer than 5 days.
- 4. Grade 3 thrombocytopenia with bleeding or grade 4 thrombocytopenia.
- Any grade 3 or 4 non-hematologic toxicity per NCI CTCAE v4.1 criteria that are probably or definitely related to study therapy, except for alopecia, nausea, and vomiting.

4.2.4. Evaluation of Response to Cetuximab and Nivolumab

During the treatment, a complete history and physical (including weight) and tumor assessment by physical examination on Day 1 of each cycle will be performed and documented. Complete blood count with differential and a comprehensive metabolic profile will be performed every 2 weeks. Radiological response will be assessed every 6 weeks by CT or MRI scans during Cycle 1-4, every 8 weeks during Cycle 5-6 and then every 12 weeks during Cycle 7-24.

4.3 DOSE LEVELS

All toxicities should be graded according to the Common Terminology Criteria for Adverse Events (version 4.1).

4.3.1. Phase I

			Cetuximab –	Nivolumab –
	Cetuximab –	Nivolumab –	Cycle 1 Day 1	Cycle 1 Day 1
	Lead-in Day -14	Lead-in Day -14	and all	and all
	before Cycle 1	before Cycle 1	subsequent	subsequent
	only	only	doses Q 2	doses Q 2
	_	-	weeks	weeks
Dose Level 1	500 mg/m ²	None	500 mg/m ²	240 mg
Dose Level -1	500 mg/m ²	None	250 mg/m ²	240 mg

4.3.2. Phase II

Once the MTD or the recommended phase II dose of cetuximab is determined in phase I, accrual to phase II will begin.

4.4. CETUXIMAB DOSE MODIFICATIONS

Study Number: MCC 19178

When the medications need to be held for toxicity reasons, both cetuximab and nivolumab are always held together and restart together.

IND#: Exempt

In cases where the treating physician delays treatment for symptoms not specified in this protocol, if such delays are documented as having been instituted in the patient's best interest this will not constitute a protocol deviation. If a patient is unavailable due to hospitalization, this too will not be considered a deviation from the protocol.

4.4.1. Dose Modifications for Cetuximab-related Immunological Toxicities

If the patient experiences any drug-related event \leq Grade 2, the dose of cetuximab and nivolumab should be continued at the given dose level.

If the patient experiences any drug-related event ≥ Grade 3, the dose of cetuximab and nivolumab should be discontinued until resolution of the toxicities to grade 1 or baseline. Upon restarting, the physician may choose to reduce the dose of Cetuximab per the dose reduction table below.

In the event of a prolonged (≥7 consecutive days) Grade 2 drug-related toxicities, the investigator may choose to pause cetuximab and nivolumab for up to 4 weeks to allow the patient to recover followed by a dose reduction (the hold and reduction are both at the treating physician's discretion). Only the cetuximab may be dose reduced, and dose reductions are according to the following table:

	Cetuximab	Nivolumab
	Cycles 1-24 (Q 2 weeks)	Cycles 1-24 (Q 2 weeks)
Dose Level 1	500 mg/m ²	240 mg
Dose Level -1	250 mg/m ²	240 mg
Dose Level -2	125 mg/m ²	240 mg

For cetuximab-related toxicity, treatment with oral/IV corticosteroids is allowed only for toxicities ≥ Grade 3.

Use of corticosteroids (≤ 10 mg daily prednisone equivalents) is allowed. Inhaled or topical steroids and adrenal replacement doses > 10 mg daily prednisone equivalents are permitted in the absence of active autoimmune disease.

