4.4.2. Dose Modifications for Cetuximab-related Non-Immunological Toxicities

If the patient experiences any drug-related event \leq Grade 2, the dose of cetuximab and nivolumab should be continued at the given dose level.

If the patient experiences any drug-related event ≥ Grade 3, the dose of cetuximab and nivolumab should be discontinued until resolution (to baseline) of the toxicities, or until stabilization. Upon resumption, the physician may choose to reduce the dose of Cetuximab per the table below. As an exception, continued treatment in the face of Grade 3 hypomagnesemia and hypophosphatemia will be allowed at the treating physician's discretion. Low magnesium is expected while treating with cetuximab and can be safely replenished as needed throughout treatment according to local guidelines.

If the patient experiences any acute onset or worsening pulmonary symptoms, the doses of cetuximab and nivolumab should be delayed. The management should follow the pulmonary toxicity management as detailed in Section 4.5 Table 2 Pneumonitis and Appendix 4 Pulmonary Adverse Event Management Algorithm because interstitial lung disease from cetuximab and pneumonitis from nivolumab cannot be reliably distinguished.

IND#: Exempt

In the event of Grade ≥ 3 rash, treatment with cetuximab should be paused until recovery to Grade ≤ 2 . Treatment should be resumed at a reduced dose (see Section 4.3). If Grade ≥ 3 rash does not resolve to Grade ≤ 2 within 14 days of stopping cetuximab treatment and despite optimal supportive care, the patient should not receive any further treatment with cetuximab.

In the event of a prolonged (≥7 consecutive days) Grade 2 drug-related toxicities, the investigator may choose to pause cetuximab and nivolumab for up to 4 weeks to allow the patient to recover followed by a dose reduction (the hold and reduction are both at the treating physcian's discretion). Only the cetuximab may be dose reduced, and dose reductions are according to the following table:

	Cetuximab	Nivolumab
	Cycles 1-24 (Q 2 weeks)	Cycles 1-24 (Q 2 weeks)
Dose Level 1	500 mg/m ²	240 mg
Dose Level -1	250 mg/m ²	240 mg
Dose Level -2	125 mg/m ²	240 mg

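### For a first Grade 3 renal event of shared or uncertain cause, sections 4.4.1 and 4.4.2 let nivolumab restart at full dose, while Table 2 requires it to stop permanently

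*Combined protocol and SAP*

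**What the plan says.** Sections 4.4.1 and 4.4.2 have headings limited to cetuximab-related toxicity, immunological and non-immunological respectively. Their dosing sentences are broader. In 4.4.1 the rule opens "If the patient experiences any drug-related event" and, at Grade 3 or higher, states that "the dose of cetuximab and nivolumab should be discontinued until resolution of the toxicities to grade 1 or baseline". It continues: "Upon restarting, the physician may choose to reduce the dose of Cetuximab per the dose reduction table below". The parallel rule in 4.4.2 is that "the dose of cetuximab and nivolumab should be discontinued until resolution (to baseline) of the toxicities, or until stabilization", followed by "Upon resumption, the physician may choose to reduce the dose of Cetuximab per the table below". In both sections "Only the cetuximab may be dose reduced, and dose reductions are according to the following table", and that table keeps nivolumab at 240 mg at dose levels 1, -1 and -2.

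The introduction to 4.4, repeated in 4.5, links the drugs: when held for toxicity, "both cetuximab and nivolumab are always held together and restart together".

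Section 4.5 says that nivolumab is held according to Table 2, whose title limits it to nivolumab drug-related events. The renal row calls for a hold at Grade 2 and permanent discontinuation at Grade 3-4, with no exception. The hepatic row (AST, ALT or bilirubin) also calls for permanent discontinuation at Grade 3-4 but points to exceptions. Footnote 1 then gives a separate stopping rule for patients with liver metastasis who start at Grade 2 AST or ALT.

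Section 4.4.2 sends acute or worsening pulmonary symptoms to Table 2 and Appendix 4 "because interstitial lung disease from cetuximab and pneumonitis from nivolumab cannot be reliably distinguished". The text has no matching sentence for renal or hepatic events.

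**The concern.** Both drugs are given together every two weeks, so the cause of many Grade 3 events will be shared or unclear. Section 7.2.4 does not help: it records causality as yes or no for the investigational product and gives no rule for dividing it between the two drugs. For a renal event of this kind, an investigator can read 4.4.1 or 4.4.2 as permission to resume both drugs after recovery. If the event is classed as non-immunological, 4.4.2 allows this once it has merely stabilized. Table 2 says that nivolumab must not be given again. The linkage rule adds to the risk, because an investigator who resumes cetuximab under 4.4 is pointed towards resuming nivolumab with it, and at full dose.

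This is a matter of patient safety and of consistent treatment across three sites. It has no bearing on the one-sample survival comparisons.

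**Working it through.** No formula applies and the plan gives no figure to reproduce. The check is a comparison of rules.

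**Step 1. Which Table 2 rows stop nivolumab permanently at a first Grade 3 event?**

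| Table 2 row | Rule at first Grade 3 | Permanent stop? |
|---|---|---|
| AST, ALT, bilirubin | Discontinue (with exceptions) | Yes |
| Diarrhea/colitis | Hold | No |
| Hyperthyroidism | Hold | No |
| Hypothyroidism | Continue with replacement | No |
| Hypophysitis | Hold, or continue with replacement | No |
| Infusion reaction | Discontinue | Yes |
| Pneumonitis | Discontinue | Yes |
| Renal failure or nephritis | Discontinue | Yes |
| All other | Hold | No |

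That is 4 of 9 rows.

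**Step 2. Which of the four are settled elsewhere?** Section 3.3.4 bars further cetuximab and further nivolumab after a Grade 3 or 4 infusion reaction. Section 4.4.2 routes pulmonary symptoms to Table 2. So 4 - 2 = 2 rows remain: renal and hepatic.

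**Step 3. Renal, side by side (first Grade 3 event, cause shared or uncertain).**
- 4.4.1, if classed as immunological: stop both drugs, restart permitted at grade 1 or baseline.
- 4.4.2, if classed as non-immunological: stop both drugs, restart permitted at baseline or on stabilization.
- Nivolumab dose on restart: 240/240 = 100% of the starting dose at each of the three dose levels.
- Table 2: permanent nivolumab discontinuation, no exception.

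The first two permit what the last forbids.

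**Step 4. Hepatic, side by side.**
- 4.4.1 or 4.4.2: as above. Section 4.2.3 lists hepatitis among the immune-related toxicities, so 4.4.1 and its stricter recovery condition would be the natural route for that diagnosis.
- Table 2: permanent discontinuation at Grade 3-4, apart from the footnote 1 subgroup.
- Appendix 4, hepatic algorithm footnote: immuno-oncology therapy may be delayed instead of discontinued at AST/ALT ≤ 8 x ULN or total bilirubin ≤ 5 x ULN. The flowchart it belongs to is not shown, so the grade it attaches to cannot be read.

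Here three texts differ, and one of them already tolerates delay for some events.

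**Step 5. Do the general stopping rules close the gap?** Sections 3.3.4 and 9.1.3 end therapy for unacceptable toxicity but define it by neither organ nor grade. The note under Table 2 covers severe or Grade 3 events that recur and life-threatening events. A first Grade 3 renal event that is not life-threatening is stopped only by its own row.

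**The case against.** The strongest reply is that Table 2 governs nivolumab and the protocol says so. Section 4.5 states that nivolumab is held for drug-related toxicities according to Table 2, and that sentence is not confined to events caused by nivolumab alone. Sections 5.2.5.1 and 5.2.5.2 both point to section 4.5 for toxicities after nivolumab, and 4.5.1 names renal and hepatic among the groups with management algorithms. Table 2 is specific to organ and grade, whereas 4.4.1 and 4.4.2 are general and sit under cetuximab headings. On that view, drug-related in 4.4 simply means cetuximab-related. Restart is also permitted, not ordered.

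Much of this stands. It shows that Table 2 is the better reading and confines the problem to events of shared or uncertain cause. It does not remove the problem. The 4.4 rules set nivolumab dosing expressly. Section 4.4.1 uses the narrower cetuximab-related term when it limits corticosteroids but not in its dosing rule. And the authors thought an explicit pointer to Table 2 was needed for the lung.

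A second reply is that the pulmonary sentence exists because both drugs are said to affect the lung, while the visible text never says that cetuximab harms liver or kidney. This is fair: the missing sentence does not prove an oversight. The finding therefore rests on the wording of the rules and makes no claim about cetuximab's toxicity.

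A third reply, that the hepatic rules are not a plain contradiction, is correct and is reflected in the verdict.

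**Conclusion.** The point holds for a first Grade 3 renal event of shared or uncertain attribution: a stated permission to restart both drugs meets a stated permanent stop for nivolumab. The headings and section 4.5 favour Table 2, but no explicit tie-break exists outside pulmonary events. Hepatic events are a weaker second case. This is a minor-to-moderate safety clarification. How many patients it would touch cannot be derived from the documents.

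The conclusion assumes that a site takes the wording of 4.4.1 or 4.4.2 literally and that the event is not clearly due to one drug.

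A reader might infer more than the documents support:
- **That hepatic and renal events are equally contradictory.** They are not, given footnote 1 and the Appendix 4 allowance for delay.
- **That sites are told to restart nivolumab.** They are only permitted to, and a cautious site could apply Table 2 without breaching 4.4.
- **That any such event may be rechallenged on stabilization.** That route exists only in 4.4.2, for non-immunological toxicity.
- **That the conflict extends to Grades 2 and 4.** The wording differs there too, but Table 2's scope with the hold-together rule largely settles Grade 2, and the life-threatening-event note largely settles Grade 4.
- **That the survival results are affected.** Nothing in the documents supports this.

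Whether cetuximab may continue alone after a permanent nivolumab stop is also left unsaid, but that is missing detail and forms no part of this finding.

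**What to change.** Amend the wording in three places.

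1. In 4.4.1 and 4.4.2, limit the Grade 3 or higher restart rules to events attributed to cetuximab alone.
2. Extend the pulmonary sentence in 4.4.2 so that any renal or hepatic event not clearly due to cetuximab alone follows Table 2 for nivolumab.
3. Reconcile the Table 2 hepatic row and its footnote 1 with the Appendix 4 hepatic footnote, stating when delay is allowed and when the stop is permanent.

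The cost is amendment text and notice to the three sites, with no extra patients or procedures. The downside is possibly a few more permanent nivolumab discontinuations than under a literal reading of 4.4.
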